### B.1.11 Power Size/Sample Size Calculations

Power assessment proceeded as follows, using a Monte Carlo approach. We used available data to define a baseline period of 10/1/2015-12/31/2016 in a bootstrap procedure. Individuals were selected with replacement from within each hospital, once to represent baseline data and separately to represent

intervention period data. In the randomization portion of the Monte Carlo approach, we ordered the hospitals by “size”, meaning the number of admissions with pneumonia. Then, within strata of 6 hospitals, we ordered by ES-DOT per at-risk day. Then we took pairs of hospitals with adjacent ES-DOT per at-risk day and assigned one member of the pair to one arm. To do this, a single pseudo-random number uniformly distributed between 0 and 1 was generated for each pair. If it was less than 0.5, the arbitrary “first” member of the pair was assigned to Routine Care and the other to Intervention. If it was greater than or equal to 0.5, then the assignments were reversed. The remaining unpaired hospital of the 59 units were assigned as the “first” member of a pair with no match. (Three sets of hospitals each shared a stewardship program and these hospitals were treated as a single hospital within the routine.)

If an admission was in the intervention arm in the intervention period, then their ES-DOT per at-risk day was reduced by a proportion, given below. The reduction of ES-DOT per at-risk day was selected with a lower bound determined by the investigators as the hoped-for effect of the intervention with minimal clinical significance, and the impact in the Monte Carlo calculation on a per-admission basis was to reduce the days of therapy proportionately between this number and 1, on a uniform distribution. In other words, if the effect of the intervention was to multiply doses by as little as .9, each person would have their doses multiplied by between .9 and 1. Then an integer value of doses would be chosen as described above.

We are interested in determining whether the patient-specific CPOE intervention reduces ES-DOT per at-risk day by at least 12.5% relative to usual care. Using the method above, we have 97% power (CI 91-99%) to detect this effect. **Table 5** below shows the calculated power and confidence intervals for the primary and secondary outcomes to be evaluated in our primary manuscript.

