The unit of analysis will be individual admissions. Individuals can contribute more than one admission. The analytic model will be a generalized linear mixed effects model for differences in differences, with random effects accounting for correlation within cluster, period-varying random effects to allow for differences between hospitals from baseline to follow-up, and admission-level random effects to account for correlation within person and hospital. Analyses of the baseline data, performed before randomization, found no evidence of overdispersion in a Poisson model, and so we plan to use that model for analysis of outcomes. The model can be expressed as follows:

$$log(y_{ijph}) = \beta_0 + \beta_1 A_{ijph} + \beta_2 T_{ijph} + \beta_3 A_{ijph} T_{ijph} + b_{0h} + b_{1h} T_{ijph} + g_i$$

where y_{ijph} is the ES-DOT per at-risk day for patient i for admission j in period p at hospital h, and $A_{ijph}=1$ if hospital h is in the intervention arm and 0 if not, and $T_{ijph}=1$ if p is the intervention period and 0 if baseline period. The random effects b_{0h} and b_{1h} allow for different baseline mean admission-level ES-DOT per at-risk day for each hospital and each hospital per period, respectively, while g_j allows different admissions to have different mean ES-DOT per at-risk day across multiple admissions. Equivalently, they allow for correlation within hospital at different levels at baseline and at follow-up.

The assessment of trial success will be determined by the significance of the arm by period interaction term β_3 , which assesses whether the log relative rate of the outcome due to being in the intervention arm in the intervention period is different from 0. The exponentiated parameter estimate for β_3 is the estimated relative rate of ES-DOT per at-risk day due to the intervention, relative to the baseline period. For example, if β_3 had a negative value and a p-value <0.05, we would conclude that the patient-specific CPOE smart prompts generated a benefit over routine care. Exponentiating the parameter value would provides an estimate of the relative reduction due to the intervention in the expected ES-DOT per at-risk day.

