The primary trial analysis will use an as-randomized unadjusted model with two-tailed significance set at alpha = 0.05. Secondary outcomes also will be assessed using an as-randomized unadjusted model with adjustment for multiple comparisons with two-tailed significance set at alpha = 0.025 for the two secondary outcomes. Subsequent analyses of the primary and secondary outcomes will include both as-treated and adjusted models. Adjusted models will account for individual characteristics such as age, gender, comorbidities, and prior history of MDROs as well as hospital characteristics such as hospital antibiotic resistance. We will also account for randomization unit and for seasonality. These analyses will be reported as point estimates with confidence intervals without p-value. The reason for including these analyses is to provide additional information related to the trial outcomes for readers to assess the effects of potential confounders. The reason to not include them in a formal multiple comparisons adjustment is because these analyses are non-independent evaluations relative to the as-randomized unadjusted analyses.

Safety outcomes noted in the above table will be assessed in the most conservative manner to identify potential safety issues. This is required because a reduction in ES-DOT might be achieved only by incorrectly withholding ES antibiotics when they were really needed. Each safety outcome will be evaluated for non-inferiority using an as-randomized unadjusted model with a one-tailed significance set at alpha = 0.05. Analyses planned for these assessments are proportional hazards models with random effects (to account for hospital effects). These models are sometimes called frailty or shared frailty models. Because these are safety outcomes, we do not intend to make adjustments for multiple comparisons in testing them, further increasing conservatism.

All analyses will be performed using current versions of SAS (Version 9.4, as of writing, SAS Institute, Cary NC) and/or R (Version 4.0, as of writing).

Power Size/Sample Size Calculations

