Power assessment proceeded as follows, using a Monte Carlo approach. We used available data to define a baseline period of 10/1/2015-12/31/2016 in a bootstrap procedure. Individuals were selected with replacement from within each hospital, once to represent baseline data and separately to represent intervention period data. In the randomization portion of the Monte Carlo approach, we ordered the hospitals by "size", meaning the number of

admissions with pneumonia. Then, within strata of 6 hospitals, we ordered by ES-DOT per atrisk day. Then we took pairs of hospitals with adjacent ES-DOT per at-risk day and assigned one member of the pair to one arm. To do this, a single pseudo-random number uniformly distributed between 0 and 1 was generated for each pair. If it was less than 0.5, the arbitrary "first" member of the pair was assigned to Routine Care and the other to Intervention. If it was greater than or equal to 0.5, then the assignments were reversed. The remaining unpaired hospital of the 59 units were assigned as the "first" member of a pair with no match. (Three sets of hospitals each shared a stewardship program and these hospitals were treated as a single hospital within the routine.)

If an admission was in the intervention arm in the intervention period, then their ES-DOT per at-risk day was reduced by a proportion, given below. The reduction of ES-DOT per at-risk day was selected with a lower bound determined by the investigators as the hoped-for effect of the intervention with minimal clinical significance, and the impact in the Monte Carlo calculation on a per-admission basis was to reduce the days of therapy proportionately between this number and 1, on a uniform distribution. In other words, if the effect of the intervention was to multiply doses by as little as .9, each person would have their doses multiplied by between .9 and 1. Then an integer value of doses would be chosen as described above.

We are interested in determining whether the patient-specific CPOE intervention reduces ES-DOT per at-risk day by at least 12.5% relative to usual care. Using the method above, we have 97% power (CI 91-99%) to detect this effect. Table 4 below shows the calculated power and confidence intervals for the primary and secondary outcomes to be evaluated in our primary manuscript.

Table 4. Power Calculation – Primary and Secondary Outcomes

Primary Trial Outcome	Power (CI), %

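### The power simulation contains no hospital-by-period variance although the primary model fits it, so 97/92/84% does not describe the planned test; whether it is too high or too low for a 12.5% reduction cannot be told from the text

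*SAP*

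**What the plan says.** Protocol B.1.11 and the SAP section Power Size/Sample Size Calculations describe the same Monte Carlo procedure.

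- **Data.** One window is named: "We used available data to define a baseline period of 10/1/2015-12/31/2016 in a bootstrap procedure". Both periods come from it: "Individuals were selected with replacement from within each hospital, once to represent baseline data and separately to represent intervention period data".
- **Effect.** The only change made to the resampled data applies to admissions in the intervention arm and period. Its effect is to "reduce the days of therapy proportionately between this number and 1, on a uniform distribution". In the worked example, "each person would have their doses multiplied by between .9 and 1". The bound is described as the effect the investigators hoped for, but its value is not given.
- **Integer step.** "Then an integer value of doses would be chosen as described above". No such step is described above that sentence.
- **Result.** Interest is in a reduction "by at least 12.5% relative to usual care". Power is given as 97% (91-99) for the primary outcome, 92% (85-96) for vancomycin and 84% (77-91) for antipseudomonals (Protocol Table 5, SAP Table 4).

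The planned model (Protocol B.1.10; SAP, Primary Statistical Analysis) includes "period-varying random effects to allow for differences between hospitals from baseline to follow-up", written b_1h, and trial success is judged on the arm-by-period interaction. The secondary outcomes are tested with "two-tailed significance set at alpha = 0.025 for the two secondary outcomes".

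**The concern.** Two samples drawn from the same hospital's records over the same 15 months share one underlying mean. In the simulation a hospital's prescribing therefore changes between periods only through sampling noise and the imposed effect. In the trial, the baseline (April 2017 to September 2018) and intervention (April 2019 to June 2020) periods have midpoints about 22 months apart, and the model allows each hospital its own change. That variance enters the standard error of the interaction directly, and more admissions per hospital do not average it away.

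The same paragraph leaves the simulated effect unclear. A multiplier uniform between a bound and 1 gives a mean reduction of half the distance to the bound, but the power is quoted for 12.5% without saying whether that is the bound or the mean.

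At stake is the reading of the power table. If the result is null, readers will use 97% to judge whether the trial could have found a 12.5% reduction, and the figure cannot carry that use as it stands.

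**Working it through.** **What can be reproduced.** The 97% cannot be rebuilt. The documents do not give hospital volumes, ES-DOT distributions, the model fitted in each replicate, its alpha, the bound, the integer rule or the number of replicates. The intervals can be checked. With 100 replicates, 97/100 has a Wilson 95% interval of 91.5-99.0% and 92/100 one of 85.0-95.9%; the normal interval for 84/100 is 76.8-91.2%. The published intervals are about this wide, so Monte Carlo error alone is several points.

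**Mean effect.** The documents' example, 0.9 to 1, has a mean reduction of (1 - 0.9)/2 = 5%. A bound of 0.875 gives 0.125/2 = 6.25%. A mean of 12.5% needs a bound of 0.75, a figure that appears nowhere.

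**Adding the missing variance.** Inputs from the documents: 59 units (taken here as 30 and 29), stated power, two-sided alpha 0.05 for the primary outcome. Assumed: tau, the SD of b_1h on the log scale, at 0.05 to 0.20. By normal approximation:

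- SE0 = |ln(1 - simulated reduction)| / (1.960 + z_power), with z_power = 1.881 for 97%
- SE = sqrt(SE0² + tau² × (1/30 + 1/29)), where 1/30 + 1/29 = 0.0678
- power = Φ(|ln(1 - true reduction)|/SE - 1.960)

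At tau = 0 this returns 97% for the simulated effect by construction.

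*Mean simulated 6.25%.* SE0 = 0.0645/3.841 = 0.0168. At tau 0.10, SE = sqrt(0.000282 + 0.000678) = 0.0310. Power for a true 12.5% is Φ(0.1335/0.0310 - 1.960) = 99%; for 6.25% it is Φ(0.0645/0.0310 - 1.960) = 55%.

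*Mean simulated 12.5%.* SE0 = 0.1335/3.841 = 0.0348. At tau 0.10, SE = 0.0434 and power is Φ(0.1335/0.0434 - 1.960) = 87%.

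| Primary outcome, power (%) | tau 0 | 0.05 | 0.10 | 0.15 | 0.20 |
|---|---|---|---|---|---|
| Mean 6.25% simulated, true 12.5% | 100 | 100 | 99 | 88 | 68 |
| Mean 6.25% simulated, true 6.25% | 97 | 86 | 55 | 33 | 22 |
| Mean 12.5% simulated, true 12.5% | 97 | 95 | 87 | 72 | 57 |

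**Where the direction changes.** If the mean simulated was 6.25%, power for a true 12.5% equals 97% when SE = 0.1335/3.841 = 0.0348. That is tau = sqrt((0.0348² - 0.0168²)/0.0678) = 0.117, or 0.11 to 0.12 across the published interval of 91-99%. Below that tau, 97% is too low for 12.5%; above it, too high.

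**Secondary outcomes.** The alpha used in the simulation is not stated. If it was 0.05, power at the planned 0.025 is Φ(1.960 + z_power - 2.241) even at tau 0: about 87% for vancomycin (z_power 1.405) and 76% for antipseudomonals (z_power 0.994), instead of 92% and 84%.

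**Integer step.** With an assumed multiplier uniform on 0.875 to 1, rounding to the nearest integer leaves any admission with 1 to 4 days of therapy unchanged, since 4 × 0.875 = 3.5. Random rounding in proportion preserves 6.25%. Rounding down turns 1 day into 0. The unstated rule can therefore move the realised effect a long way.

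**The case against.** The strongest reply is that 97% may be conservative. The text sets the bound as the hoped-for effect and names no effect other than 12.5%, so 0.875 is the natural bound. On that reading power for a true 12.5% stays above 97% until tau is about 0.12, and above 80% until about 0.17. This stands, and it is why no direction is claimed for 12.5%. It does not settle the matter, because the bound is not stated and tau is unknown.

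Materiality is also open. If 12.5% was the mean simulated, tau 0.05 takes 97% only to 95%, inside the published interval. If 15-month volumes were drawn for both periods (not stated), the real 18-month baseline scales SE0 by sqrt((1/18 + 1/15)/(2/15)) = 0.957, which lifts 97% to about 98%. Both points stand as limits on size.

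On timing, the SAP is dated June 3, 2020, weeks before the intervention period ends, so a re-run cannot change the number of hospitals. The 2017-2018 baseline was also incomplete at the protocol date (7/3/2018). Both are true; the remedy corrects a reported design figure and does not alter the design.

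A reader might infer that the trial is underpowered, or that the primary test is invalid. The documents support neither: the first needs a tau and a simulated mean that they do not give, and the planned analysis already fits b_1h.

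**Conclusion.** The concern holds in a limited form. The simulation omits a variance component that the primary model includes and that bears directly on the interaction, so 97/92/84% does not describe the planned test.

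The figures are upper limits only for the mean effect actually simulated, and only if:
- units, admission volumes and ES-DOT levels are as in 2015-2016;
- the model fitted in each replicate was no less powerful than the planned one;
- the simulation's alpha was no stricter than planned; and
- Monte Carlo error is set aside.

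For the 12.5% target the sign of the error is not established. The powers computed here rest on an assumed tau and a normal approximation; they show sensitivity and should not be quoted as corrected powers. The estimand, the test and the type I error are unaffected. Confidence is medium: the single window is plain in the text, but the size of its effect is not.

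**What to change.** Re-run the simulation and restate Protocol Table 5 and SAP Table 4.

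- Draw the two periods from different pre-intervention windows of the same hospitals, for example 10/2015-12/2016 and 4/2017-9/2018, both complete by the SAP date. Alternatively, add b_1h with an SD estimated from such windows.
- Fit the planned model in each replicate.
- Set the mean simulated reduction to 12.5%, or state power for the mean actually simulated. Give the bound and the integer rule.
- Use alpha 0.025 for the secondary outcomes, and state the alpha used.
- Use about 1000 replicates, which gives 1.96 × sqrt(0.97 × 0.03/1000), or about ±1 point at 97%, and about ±2 points at 84%.
- Show power over a range of tau.

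The cost is computing time. No hospitals are added and the planned analysis does not change. The downside is a stated power that may be less favourable.
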